## 6. GENERAL ISSUES FOR STATISTICAL ANALYSIS

### 6.1. Statistical Definitions and Algorithms

#### 6.1.1. Baseline

For assessments where time was recorded (e.g., ECG), the last observation recorded before the first application of study drug will be used as the baseline observation for all calculations of change from baseline. For assessments where time was not recorded (excluding WI-NRS and Pain NRS), the last observation recorded on or before the day of first application of study drug will be used as the baseline observation for all calculations of change from baseline. For WI-NRS and Pain NRS, since diaries were completed daily at home from the Baseline/Day 1 visit until end of treatment, baseline is defined as the last observation recorded before the day of first application of study drug.

For assessments that are collected both before and after application of study drug at the Baseline/Day 1 visit, the last observation recorded before the first dose of study will be used as the baseline observation. For assessments collected only after application of study drug, no baseline will be defined (except for subject local tolerability; in this case, baseline is defined as the first non-missing observation recorded after the first application of study drug). If the tolerability assessments are not done as per [protocol Section 5.1.7](#), those records will be excluded from the analysis.

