- ^e BSA will be measured as the affected BSA for each side of each hand. Affected areas of the lateral aspects of the fingers and hands should be assigned to the palmar surface. IGA will be a 5-point scale ranging from clear (0) to severe (4). **IGA should be completed prior to other physician assessments and by the same Evaluator at each study visit.** HECSI is an instrument used in clinical trials to rate the severity of 6 clinical signs of hand eczema and the extent of the lesions on each of 5 distinct hand anatomic areas by use of standard scales. The total HECSI score is based on a 4-point clinical sign severity scale ranging from 0 (none/absent) to 3 (severe) and a 5-point scale rating the different affected hand anatomic area(s) ranging from 0 (0% affected area) to 4 (76% to 100% affected area).
- ^f Subjects will complete the WI-NRS pruritis assessment and NRS Pain assessment in the clinic during screening and then daily at home from the Baseline/Day 1 visit through the Day 15 visit.
- ^g A serum pregnancy test will be administered to all females of child-bearing potential at Screening. A urine pregnancy test will be administered at Visits 2, 4, 5, and 7 to all females of childbearing potential. A negative result is required for continued participation in the study, and results must be available prior to dispensing of investigational product.
- ^h FSH will be performed (if indicated) at Screening to confirm post-menopausal status.
- ⁱ On the first day of dosing (Day 1), PK samples will be collected at 1, 2, 4, 6 (all +/- 10 mins) and 24 hours post-dose administration (Day 2, +/- 2 hours). On Day 15 (last dose application), PK samples will be collected pre-dose, 1, 2, 4, 6, (all +/- 10 mins) and 24 hours post dose administration (Day 16, +/- 2 hours). For 24-hour timepoints, subjects return to the clinic on the following day within 2 hours of the IP application time from the previous day for pre-dose PK plasma sample. A pre-dose PK sample will be taken at Day 8.
- ^j Clinic personnel will apply assigned IP on Visits 2, 4 and 5 (Baseline, Day 8 and Day 15). Every tube should be weighed before and after IP application and weights recorded. For the 24-hour PK sampling timepoint the application of investigational product should occur after the PK sample has been collected.
- ^k Subject should return with investigational product kit at each Visit. Every tube should be weighed before and after use and weights recorded when dispensed and returned.

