- ^e Subjects will complete the WI-NRS pruritis assessment and NRS Pain assessment in the clinic during Screening and then daily at home from the Baseline/Day 1 visit until the Week 13 visit. QOLHEQ = Quality of Life in Hand Eczema Questionnaire will be completed at each visit.
- ^f Assessment of nail dystrophy including Baseline identification of the nail with the worst dystrophy and measurement of the millimeters of normal appearing nail distal to the cuticle post Baseline. Sites participating in optional photography will obtain photos of nail with the worst dystrophy at Baseline/Day 1 and at subsequent visits. See [Section 5.2.7](#) for details.
- ^g Local tolerability assessments to be recorded prior to IP application for the Investigator assessment of skin irritation (Berger and Bowman skin irritation score) and 10-15 minutes post IP application for the subject's '0-3' burning/stinging assessment. **Note for investigator tolerability assessments: reactions at the site of IP application, which may occur post-Baseline, should be differentiated from the preexisting inflammation associated with the subject's chronic hand eczema.**
- ^h Photography will be performed at selected investigational sites. Photography will be optional. All efforts will be made to de-identify the subjects. Sites participating in optional photography will obtain photos of nail with the worst dystrophy at Baseline/Day 1 and at subsequent visits.
- ⁱ A serum pregnancy test will be administered to all females of childbearing potential at Screening. A urine pregnancy test will be administered at Baseline, Weeks 4, 8, 12 and 13. A negative result is required for continued participation in the study, and results must be available prior to dispensing of investigational product.
- ^j FSH will be performed (if indicated) at Screening to confirm post-menopausal status.
- ^k PK assessments will be collected from all subjects at Days 1, 29 and 85. The draws will be pre-dose IP application in the clinic.
- ^l Subjects to apply assigned IP in clinic at these visits. The time of application will be documented.
- ^m Kits will be dispensed at Baseline, Weeks 2, 4 and 8. Dispensing at Week 12 requires approval from the Medical Monitor. See IP Handling Manual for details.

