4.3 Subject Participation

Phase 1 (Cohort 1)

Subject participation involves a minimum of 7 clinic visits including Screening, Baseline/Day 1, Day 2, Day 8, Day 15, Day 16 and Day 22. Subjects will be treated with investigational product (ARQ-252 cream 0.3% QD) for 2 weeks. The interval between the Screening and Baseline visits could be up to 4 weeks, therefore the anticipated maximum duration of subject participation is 7 weeks.

Phase 2b (Cohort 2)

Subject participation involves a minimum of 7 clinic visits including Screening, Baseline/Day 1, Week 2, Week 4, Week 8, Week 12 and Week 13. Subjects will be randomized to a treatment group and will be treated with investigational product for 12 weeks. The interval between the Screening and Baseline visits could be up to 4 weeks, therefore the anticipated maximum duration of subject participation is 17 weeks.

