4.12.2 Treatment Administration

Initial treatment with the IP will occur on Day 1. At the Baseline visit the study staff will demonstrate to the subject how to apply IP using the first tube that is assigned to the subject at enrollment/randomization. Study site staff will demonstrate how two unit doses (two pea size amounts of IP will cover approximately 4% BSA, i.e., both hands entirely) are properly squeezed from the tube and applied as a thin film to cover both hands. IP will be applied to the front and back of both hands, interlacing fingers, rubbing in thoroughly but gently, until the cream has absorbed. The subject will then practice squeezing a similar amount and applying IP. The study staff will confirm that the subject's application technique is correct.

Subjects in Cohort 1 will be instructed to apply IP once daily (QD). Subjects in Cohort 2 will be instructed to apply IP either once daily (QD) or twice daily (BID), as determined at randomization.

IP tubes must be returned by subjects at each study visit, both empty and full, and will be weighed. Re-training will be conducted at subsequent visits as needed (i.e., if the returned tube weighs substantially different than the expected weight).

Subjects will be instructed to refrain from handwashing for 4 hours after IP application, if possible. Subjects may use hand sanitizer within 4 hours of IP application, if necessary. Hand washing and use of hand sanitizer within 4 hours of IP application will be recorded in the subjects' diary and CRF.

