### 6.1.7. Derived Variables

- **Study Week** = 7-day periods starting on Day 1, as described in [Section 6.1.5.2](#). For example, Study Week 1 corresponds to Days 1 to 7. This is in contrast to **Study Visit**, which describes the actual clinic visit week. The nomenclature of “Study Week” will be used with respect Pain NRS and WI-NRS analyses; otherwise, “Study Visit” will be used.
- **IGA Improvement** = achievement of at least a 2-point improvement (i.e., reduction) in IGA score from baseline.
- **IGA Success** = post-baseline IGA of “Clear” or “Almost Clear” PLUS achievement of at least a 2-point improvement (i.e., reduction) in IGA score from baseline.
- **Average Weekly WI-NRS Pruritus Score** = WI-NRS pruritus scores will be assigned to a particular study week based on the study week window, as shown in [Section 6.1.5.2](#). If 2 or more observations are present for a single day, those observations will be averaged into a single daily value before calculating the average weekly score. The average of the reported (non-missing) WI-NRS pruritus scores assigned to each study week will be calculated. If at least 1 WI-NRS pruritus score is present in this time period, the average weekly WI-NRS pruritus score will be calculated; otherwise the average weekly score will be missing for that week.
- **WI-NRS 4-point Reduction** = achievement of a 4-point reduction in WI-NRS pruritus score at each study week compared to baseline, calculated only for subjects with a WI-NRS pruritus score of  $\geq 4$  at baseline (PRU4 population).
- **HECSI Fingertips Subscore** =  $(E + I + V + F + S + O) * Ex$ ,  
where E, I, V, F, S, and O, are erythema, infiltration/papulation, vesicles, fissures, scale, and oedema, respectively, scored on a scale of 0 to 3 (none to severe); Ex is estimated area of skin involved, graded on a scale of 0 to 4. The range for the HECSI Fingertips subscore is 0 to 72. If any of the component scores are missing, the HECSI Fingertips subscore cannot be calculated; however, if the estimated area of skin involved = 0, the HECSI Fingertips subscore will be set to 0. Lower scores indicate better outcomes.
- **HECSI Fingers (except tips) Subscore** =  $(E + I + V + F + S + O) * Ex$ ,  

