[1] Treatment received for Cohort 1 and randomized treatment for Cohort 2.

[2] IGA Score of "Clear" or "Almost Clear" ("Yes") is defined as an IGA score of "Clear" or "Almost Clear"; "No" otherwise.

[3] IGA Success ("Yes") is defined as an IGA score of "Clear" or "Almost Clear" plus a ≥2-grade improvement from baseline; "No" otherwise.

**Programming note:** For "Was Assessment Completed?" column, if answer is Yes and answer to question "Yes, did COVID-19 disruption cause or contribute to a delay in IGA Collection?" is "Yes", then display "Yes: COVID-19 Disruption Caused/Contributed to Delay in IGA Collection"; if answer to COVID-19 question is "No", only display "Yes". Similarly, for "Was Assessment Completed?" column, if answer is No and answer to question "If No, did COVID-19 disruption cause or contribute to missed IGA Collection?" is "Yes", then display "No: COVID-19 Disruption Caused/Contributed to Missed IGA Collection"; if reason IGA not completed is non-missing, concatenate that reason with the response to "No", as follows: "No: COVID-19 Disruption Caused/Contributed to Missed IGA Collection; XXXXXXXXX".

"No: XXXXXXXXX"

Listing 16.2.6.2  
Worst Itch Numerical Rating Scale (WI-NRS)  
All Subjects

Subject ID	Treatment [1]	Was Assessment Completed?	Study Week	Date of Assessment (Study Day)	Result	Change from Baseline	WI-NRS Success (Baseline ≥ 4) [2]
XXXXXX	XXXXXX	Yes	Baseline	DDMMYYYY (-1)	X		
		Yes	Week 1	DDMMYYYY (1)	X	X	
		Yes		DDMMYYYY (2)	X	X	
		Yes		DDMMYYYY (3)	X	X	
		Yes		DDMMYYYY (4)	X	X	
		Yes		DDMMYYYY (5)	X	X	
		Yes		DDMMYYYY (6)	X	X	
		Yes		DDMMYYYY (7)	X	X	
		Yes	Week 2	DDMMYYYY (14)	X	X	
		Yes	Week X	DDMMYYYY (X)	Average Weekly Score: X [3]	X	Yes
		No: COVID-19 Disruption		DDMMYYYY (X)	X	X	
		Yes	XXXX	DDMMYYYY (X)			
		No: XXXXXX	XXXX				

Abbreviations: BID = twice daily; COVID-19 = novel coronavirus disease-19; QD = once daily; WI-NRS = Worst Itch – Numeric Rating Scale.

Note: Study day is calculated relative to the date of first application of study drug. Subjects rate the intensity of their itch on an 11-point scale ranging from 0 (no itch) to 10 (worst itch imaginable). Higher score indicates greater itch intensity. Baseline is the last non-missing measurement taken on or before the day of first application of study drug. Change from baseline is calculated as result – baseline result.

[1] Treatment received for Cohort 1 and randomized treatment for Cohort 2.

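### Baseline itch and pain scores are in effect a single Screening value up to 4 weeks old, while the Day 1 score is averaged into Week 1 and two listings state a different baseline rule

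*SAP*

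**What the plan says.** SAP 6.1.1 sets a general rule for assessments without a recorded time: "the last observation recorded on or before the day of first application of study drug will be used as the baseline observation". It then exempts WI-NRS and Pain NRS because their diaries are kept at home from Day 1. For these two scales, "baseline is defined as the last observation recorded before the day of first application of study drug".

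The Cohort 2 schedule (Protocol 1.3, footnote e) has subjects score itch and pain "in the clinic during Screening and then daily at home from the Baseline/Day 1 visit until the Week 13 visit". Cohort 1 follows the same pattern: "in the clinic during screening and then daily at home from the Baseline/Day 1 visit through the Day 15 visit". Protocol 4.12.2 fixes the start of dosing: "Initial treatment with the IP will occur on Day 1". On timing, Protocol 4.3 says: "The interval between the Screening and Baseline visits could be up to 4 weeks".

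For the weekly averages, SAP 6.1.7 states: "For example, Study Week 1 corresponds to Days 1 to 7". Tables 5 and 6 of the SAP agree. One entry is enough to compute a weekly average.

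The NRS summary-table footnotes and Listing 16.2.4.1.2 follow SAP 6.1.1. The footnotes of Listings 16.2.6.2 (WI-NRS) and 16.2.6.4 (Pain NRS) do not. They read: "Baseline is the last non-missing measurement taken on or before the day of first application of study drug".

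**The concern.** IGA, HECSI, BSA and QOLHEQ are measured at the Baseline visit and may use that value. Itch and pain are the exception: their baseline comes from an earlier visit, when the subject may still have been using a topical treatment that had to stop before Baseline. Tables headed as baseline itch or pain would in fact show Screening scores, and the list of changes in SAP Section 10 does not mention this.

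Several results rest on that one score:

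- every weekly change and percent change in itch and pain;
- the one-sample P values for change;
- the 4-, 3- and 2-point responder rates;
- membership of PRU4, PNRS4, PNRS3 and PNRS2;
- the Cohort 1 NRS summaries;
- the baseline covariate in the NRS ANCOVA models.

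The Day 1 score, which asks about the previous 24 hours and may mostly describe the time before dosing, is treated as a post-baseline result.

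**Working it through.** The plan gives no figure to reproduce here. The check traces the schedule and then sizes what can be sized.

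**1. Which score qualifies as baseline.** NRS scores exist at Screening and daily from Day 1. First application is on Day 1. The rule excludes Day 1 itself. Nothing is scheduled in between, and the unscheduled-visit list in Protocol 5.6 does not include the NRS scales. Only the Screening score is left. The shell of Listing 16.2.6.2 shows a baseline entry on Day -1, a day with no scheduled collection.

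**2. How old it can be, relative to washout.** The longest Screening-to-Baseline interval is 4 weeks = 28 days. Protocol 4.7.2 and Table 2 count washouts back from Baseline (Visit 2). The Screening score can precede the latest permitted start of washout by at most 28 minus the washout length:

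| Washout | Length (days) | Maximum lead (days) |
|---|---|---|
| Low/mid-potency topical steroids, calcineurin and PDE-4 inhibitors, urea emollients, topical antibiotics | 7 | 28 − 7 = 21 |
| High-potency topical steroids | 14 | 28 − 14 = 14 |
| 28-day washouts, such as phototherapy | 28 | 28 − 28 = 0 |

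**3. Weight of Day 1 in the Week 1 average.** With k entries present, Day 1 has weight 1/k: 1/7 = 14% for a full diary, 1/3 = 33% for three entries, and 100% if it is the only one.

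**4. Precision of the ANCOVA.** This step uses assumed correlations, because the documents give none. Let r1 be the correlation of the Day 1 score with Week 12 and r0 that of the Screening score with Week 12. With one baseline covariate, the ratio of residual variances, Screening baseline against Day 1 baseline, is (1 − r0²)/(1 − r1²). Take r1 = 0.5, so the denominator is 0.75.

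- Screening predicts as well as Day 1, r0 = 0.5: 0.75/0.75 = 1.00, a 0% increase.
- Slightly worse, r0 = 0.45: 0.7975/0.75 = 1.06, a 6% increase.
- Screening predicts only through Day 1, with Screening–Day 1 correlation 0.8: r0 = 0.8 × 0.5 = 0.40, and 0.84/0.75 = 1.12, a 12% increase.
- The same with Screening–Day 1 correlation 0.4: r0 = 0.4 × 0.5 = 0.20, and 0.96/0.75 = 1.28, a 28% increase.

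**5. Agreement on the 4-point threshold.** Again on assumptions: bivariate normal scores with mean 5 and SD 2.3 at both times, correlation 0.8 to 0.4, and scores rounded to integers so that 4 or more means above 3.5. Then 16–29% of subjects fall on different sides of the threshold at Screening and on Day 1, and 11–20% of those at 4 or more at Screening are below 4 on Day 1. A cut at exactly 4.0 gives 19–33% and 14–25%.

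**6. The two written rules.** For a subject with a Day 1 entry, the rule in SAP 6.1.1 selects Screening and the rule in the two listing footnotes selects Day 1. Listed and tabulated changes would then differ for the same subject.

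**The case against.** The SAP gives a fair reason for its choice. A home diary entry on Day 1 carries no known time and may follow the first application. Section 6.1.1, the summary-table footnotes and Listing 16.2.4.1.2 agree with each other, so the two deviating listing footnotes look like an editorial slip. Four weeks is a maximum, inclusion criterion 3 asks for generally stable disease over 6 weeks, and a washout of 28 days or longer must already have begun by Screening. The stakes are limited: SAP 4.1 keeps formal testing for the primary IGA endpoint and for HECSI change, and gives other P values for information. Week 1 is a time point that the SAP added; the protocol's NRS endpoints are at Weeks 2, 4, 8 and 12. All of this stands. It limits the point without answering it, because a score taken in clinic before application would have a known timing.

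A reader might infer more than the documents support:

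- **Biased treatment comparisons.** The Screening score precedes randomisation and the rule is the same in every arm, so it does not bias the comparisons by arm.
- **A fixed precision loss of 12–28%.** That range requires Screening to carry no information on Week 12 beyond what Day 1 carries. If both scores reflect a stable level plus daily noise, the loss can be nil. The upper end also has two scores at most 4 weeks apart correlating less (0.4) than two scores 12 weeks apart across treatment (0.5), which is hard to believe. Baseline IGA category, also in the model, may absorb part of any loss.
- **Subjects in the wrong responder population.** The figures in step 5 measure disagreement between two single noisy scores. They do not show that Day 1 is right and Screening wrong, and selecting on one Day 1 score would leave regression to the mean in place.
- **Inflated improvement from a washout flare.** No document figure sizes such a flare. One arising after Screening would make change from Screening understate improvement, in all arms alike.

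**Conclusion.** The point holds as a matter of definition. Baseline WI-NRS and Pain NRS are in effect one Screening score, at most 28 days before Day 1 and possibly before the 7- or 14-day topical washouts begin. Day 1 counts as post-baseline, and the SAP states two incompatible rules. These findings need no assumption beyond the schedule being followed.

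The consequences fall on absolute NRS results, responder rates, threshold-population membership, Cohort 1 NRS summaries and the usefulness of the covariate. The primary IGA and the HECSI endpoints are untouched. The precision loss cannot be fixed from the documents: it is about 0% if Screening predicts Week 12 as well as Day 1 does, and 12–28% if it predicts only through Day 1, under the correlations assumed above. This is an inexpensive improvement to secondary endpoints and does not threaten the trial's main conclusion.

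**What to change.** **If collection can still change:** have subjects score both NRS items in clinic at the Baseline visit, before the first application, and define that as baseline, using the Screening score only if it is missing. SAP 6.1.1 and the NRS table footnotes would need the same wording. The cost is a short protocol and CRF amendment with the usual ethics approval, and mixed baselines, because subjects already enrolled keep their Screening score.

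**If it cannot:** state in SAP 6.1.1 and Section 10 that NRS baseline is the Screening score, and add a sensitivity analysis with the Day 1 score as baseline. This needs only SAP wording and modest programming. Its limit is that the Day 1 home entry may follow dosing.

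**In either case:** start the Study Week 1 average on Day 2 in SAP 6.1.7 and Tables 5 and 6, and align the footnotes of Listings 16.2.6.2 and 16.2.6.4 with SAP 6.1.1.

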5.1.7 Local Tolerability Assessment

The Investigator Local Tolerability Assessment will be performed according to the Schedule of Visits and Assessments ([Section 1.3](#)).

Application site reactions will be graded at the timepoints outlined in the Schedule of Visits and Assessments ([Section 1.3](#)). Irritation reactions are graded using the scale detailed in the following section ([Berger 1982](#)). **Reactions at the site of product application, which may occur post-Baseline, should be differentiated from the preexisting inflammation associated with the subject's chronic hand eczema.**

The Investigator assessments will be conducted by the Investigator prior to investigational product application in the clinic.

Dermal Response

- 0 = no evidence of irritation
- 1 = minimal erythema, barely perceptible
- 2 = definite erythema, readily visible; minimal edema or minimal papular response
- 3 = erythema and papules
- 4 = definite edema
- 5 = erythema, edema and papules
- 6 = vesicular eruption
- 7 = strong reaction spreading beyond application site

Other Effects

- A = slight glazed appearance
- B = marked glazing
- C = glazing with peeling and cracking
- D = glazing with fissures
- E = film of dried serous exudates
- F = small petechial erosions and/or scabs
- G = no other effects

The Subject Local Tolerability Assessment will be performed according to the Schedule of Visits and Assessments ([Section 1.3](#)).

This assessment will be administered by the site 10 to 15 minutes after investigational product application in the clinic.

Grade	Sensation Following Investigational Product Application
0 (none)	No sensation
1 (mild)	Slight warm, tingling sensation; not really bothersome
2 (moderate)	Definite warm, tingling sensation that is somewhat bothersome
3 (severe)	Hot, tingling/stinging sensation that has caused definite discomfort

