- **Number of Expected IP Applications (BID dosing)** = 170 (Cohort 2 BID) for subjects who complete the study or number of days between first and last application of IP, derived as  $2 * (\text{last treatment date} - \text{first treatment date} + 1)$ , for subjects who discontinue early from the study.
- **Number of Expected IP Applications (QD dosing)** = 30 (Cohort 1) or 85 (Cohort 2 QD) for subjects who complete the study or number of days between first and last application of IP, derived as  $(\text{last treatment date} - \text{first treatment date} + 1)$ , for subjects who discontinue early from the study.
- **Number of IP Applications** = number of expected IP applications – missed IP applications as collected in the electronic case report form (eCRF).
- **Weight of IP (g)** = returned tube weight – dispensed tube weight.
- **Body Mass Index (BMI) ( $\text{kg}/\text{m}^2$ )** =  $[\text{weight (kg)} / \text{height (cm)} / \text{height (cm)}] \times 10,000$ .
- **Change from Baseline** = value at current time point – value at baseline.
- **Treatment Emergent AE (TEAE)** = any AE with an onset date/time after the first application of IP. If time is unavailable, any AE occurring on or after the date of first application of IP will be considered treatment emergent.
- **Completion of Study** = Completion of the primary efficacy assessment (IGA) at Week 12. This may differ than what was recorded in the eCRF.

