### 13.1.3.6. Other Safety Data Summary Tables

Table Number	Population	Table Title / Summary
Table 14.3.6.1.1	Safety	Cohorts 1 and 2: Summary of Investigator Local Tolerability Assessment (Dermal Response) by Study Visit
Table 14.3.6.1.2	Safety	Cohorts 1 and 2: Summary of Investigator Local Tolerability Assessment (Dermal Response) by Study Visit Categorical Results
Table 14.3.6.1.3	Safety	Cohorts 1 and 2: Summary of Investigator Local Tolerability Assessment (Other Effects) by Study Visit Categorical Results
Table 14.3.6.2.1	Safety	Cohorts 1 and 2: Summary of Subject Local Tolerability Assessment by Study Visit
Table 14.3.6.2.2	Safety	Cohorts 1 and 2: Summary of Subject Local Tolerability Assessment by Study Visit Categorical Results
Table 14.3.6.3.1	Safety	Cohort 1: Summary of Vital Signs by Study Visit
Table 14.3.6.3.2	Safety	Cohort 2: Summary of Vital Signs by Study Visit
Table 14.3.6.4.1.1	Safety	Cohort 1: Summary of 12-Lead Electrocardiogram by Study Visit
Table 14.3.6.4.1.2	Safety	Cohort 2: Summary of 12-Lead Electrocardiogram by Study Visit
Table 14.3.6.4.2.1	Safety	Cohort 1: Summary of 12-Lead Electrocardiogram Interpretation by Study Visit
Table 14.3.6.4.2.2	Safety	Cohort 2: Summary of 12-Lead Electrocardiogram Interpretation by Study Visit
Table 14.3.6.5.1	Safety	Cohort 1: Summary of Physical Examination by Study Visit
Table 14.3.6.5.2	Safety	Cohort 2: Summary of Physical Examination by Study
Table 14.3.6.6	Safety	Cohorts 1 and 2: Summary of Concomitant Medications by ATC Class Level 4 and Preferred Term

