D = Glazing with fissures	XX (XX.X%)					
E = Film of dried serous exudates	XX (XX.X%)					
F = Small petechial erosions and/or scabs	XX (XX.X%)					
G = No other effects	XX (XX.X%)					
Week 2	XX	XX	XX	XX	XX	XX
A = Slight glazed appearance	XX (XX.X%)	XX (XX.X%)	XX (XX.X%)	XX (XX.X%)	XX (XX.X%)	XX (XX.X%)
...	XX (XX.X%)	XX (XX.X%)	XX (XX.X%)	XX (XX.X%)	XX (XX.X%)	XX (XX.X%)

*Continue for the following study visits, applicable to Cohort 2 only: Week 4, Week 8, and Week 12; put "NA" in the study visit row for Cohort 1 for these visits.*

Abbreviations: BID = twice daily; NA = not applicable; QD = once daily.  
 Note: Percentages are n/Number of subjects in the Safety Population within treatment received, study visit, and overall\* 100. The Week 1 study visit is only applicable to Cohort 1 subjects; the Week 4 through Week 12 study visits are only applicable to Cohort 2 subjects. These assessments should be done prior to the study drug application in the study site. Subjects not meeting this condition on baseline visit are completely removed from the table summary. Baseline is the last non-missing measurement taken before the first application of study drug.  
 Reference Listing: 16.2.9.1

Table 14.3.6.2.1  
Cohorts 1 and 2: Summary of Subject Local Tolerability Assessment by Study Visit  
Safety Population

(Same shell as Table 14.3.6.1.1; use the below footnotes)

Abbreviations: BID = twice daily; NA = not applicable; QD = once daily; SD = standard deviation.

Note: Subjects are summarized by treatment received. The Week 1 study visit is only applicable to Cohort 1 subjects; the Week 2 through Week 12 study visits are only applicable to Cohort 2 subjects. These assessments should be done 10 - 15 minutes after the application of study drug at the study site. Subjects not meeting this condition on baseline visit are completely removed from the table summary. Baseline is the first non-missing measurement taken after the first application of study drug. Change from baseline is calculated as result – baseline result.  
Reference Listing: 16.2.9.2

Table 14.3.6.2.2  
Cohorts 1 and 2: Summary of Subject Local Tolerability Assessment by Study Visit  
Categorical Results  
Safety Population

Study Visit Category	Cohort 1					Cohort 2		
	ARQ-252 Cream 0.3% QD (N=XX)	ARQ-252 Cream 0.3% QD (N=XX)	ARQ-252 Cream 0.3% BID (N=XX)	ARQ-252 Cream 0.1% QD (N=XX)	Vehicle Cream QD (N=XX)	Vehicle Cream BID (N=XX)		
Baseline	XX	XX	XX	XX	XX	XX		

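### The subject's burning/stinging score uses the first post-application score as its baseline, so the Change column of SAP Table 14.3.6.2.1 cannot be read as change from baseline

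*SAP*

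**What the plan says.** Protocol 5.1.7 describes a four-grade subject assessment, from 0 for no sensation to 3, worded as "Hot, tingling/stinging sensation that has caused definite discomfort". On timing it says: "This assessment will be administered by the site 10 to 15 minutes after investigational product application in the clinic". The schedule includes no score before the application.

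SAP 6.1.1 first gives a general rule: "For assessments collected only after application of study drug, no baseline will be defined". It then makes an exception for subject local tolerability: "in this case, baseline is defined as the first non-missing observation recorded after the first application of study drug". The footnote to Table 14.3.6.2.1 repeats the exception: "Baseline is the first non-missing measurement taken after the first application of study drug". It defines change as the result minus that baseline, in line with the derived-variable rule in SAP 6.1.7, "value at current time point – value at baseline".

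The layout of Table 14.3.6.2.1 is given as "Same shell as Table 14.3.6.1.1; use the below footnotes". Table 14.3.6.1.1 is the investigator's dermal-response table, and it has Observed and Change columns for each arm. A second table, "Summary of Subject Local Tolerability Assessment by Study Visit Categorical Results" (Table 14.3.6.2.2), gives counts and percentages at each grade by visit and arm. Its first row is also headed Baseline.

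**The concern.** A baseline is meant to describe the subject before treatment. Here it describes the subject's reaction to the first treatment. Subtracting it from later scores removes any part of the reaction that is present from the first application and persists. If the reaction weakens with use, the subtraction turns the first-dose reaction into an apparent gain for the arm that caused it.

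Tolerability is a safety endpoint in Cohort 2, where active cream is set beside vehicle, so a reader of the Change column there could draw the wrong comparison. The label adds to the risk. In the neighbouring investigator tables, Baseline means the last value before the first application. In the subject tables the same word means a value after it.

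**Working it through.** The documents state no figure for this point, so the check applies the SAP's own definitions to possible score records.

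**Inputs**
- Score range 0 to 3, taken after application (protocol 5.1.7).
- Cohort 2 assessments at Day 1 and Weeks 2, 4, 8 and 12 (schedule of visits).
- Baseline = first post-application score, S(1) (SAP 6.1.1 and the Table 14.3.6.2.1 footnote).
- Change at visit t = S(t) - S(1) (SAP 6.1.7).

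**Single-subject records (hypothetical)**

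| Record | Observed, Day 1 to Week 12 | Change at Weeks 2, 4, 8, 12 | Mean observed after Day 1 |
|---|---|---|---|
| Never stings | 0,0,0,0,0 | 0,0,0,0 | 0 |
| Mild every time | 1,1,1,1,1 | 0,0,0,0 | 1 |
| Moderate every time | 2,2,2,2,2 | 0,0,0,0 | 2 |
| Severe every time | 3,3,3,3,3 | 0,0,0,0 | 3 |
| Severe, then mild | 3,1,1,1,1 | -2,-2,-2,-2 | 1 |
| None, then mild | 0,1,1,1,1 | 1,1,1,1 | 1 |

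The first four records have the same Change values although their later observed scores range from 0 to 3. The second, fifth and sixth have the same later scores, yet their Change values are 0, -2 and +1.

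**Between arms.** Let vehicle score s throughout.
- Active cream scores s + d at every visit. Change is (s + d) - (s + d) = 0 on active and s - s = 0 on vehicle. The difference in Change is 0, while the difference in observed score is d at every visit.
- Active cream scores s + d on Day 1 only and s afterwards. Change is s - (s + d) = -d on active and 0 on vehicle. Active appears better by d at every later visit, when the two arms in fact score the same.

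**Missing or mistimed Day 1 score.** Three pieces of text bear on this.
- SAP 6.1.1 excludes tolerability records not done according to protocol 5.1.7.
- SAP 6.1.1 also takes the first non-missing score as baseline. Read literally, a subject with no usable Day 1 score but a Week 2 score w has baseline w and Week 2 change w - w = 0.
- The footnotes to Tables 14.3.6.2.1 and 14.3.6.2.2 remove a subject entirely if the baseline-visit assessment misses the timing condition.

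The texts thus differ on whether the record or the whole subject is dropped. They do not say whether an absent Day 1 score counts as failing the timing condition.

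**The case against.** The strongest reply is that nothing is concealed. Table 14.3.6.2.1 prints Observed beside Change, so the mean, median and range of the raw scores appear by arm at Day 1 and at every later visit. Table 14.3.6.2.2 adds the full grade distribution, including the first application. A contrast of 3,3,3,3,3 with 0,0,0,0,0 is plain in both. SAP 9.2 plans no inferential test, and neither it nor protocol 6.3.2 makes change from baseline the tolerability analysis. All of this stands. A reader might infer from the arithmetic that the trial could miss a cream that stings constantly, but the planned observed summaries rule that out.

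A reader might also tie the point to the primary endpoint of Cohort 1, of which tolerability is a part. Cohort 1 is open label, with one arm and about 6 subjects, so it has no vehicle contrast to lose. Its Change column has the same meaning problem, but the between-arm argument belongs to Cohort 2.

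Nor do the documents establish that Week 2 becomes the baseline whenever Day 1 is unusable. The footnotes remove subjects who fail the timing condition at the baseline visit. What can be shown is an unresolved difference between the two texts.

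Finally, the exception is deliberate and disclosed, and change from the first application is a readable way to see whether sensation builds or fades. That is a fair reason to keep the quantity under an accurate name. It does not justify calling it change from baseline.

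**Conclusion.** The point holds in a limited form. The Change column of Table 14.3.6.2.1 subtracts a treatment effect, so constant stinging and no stinging both give 0, and a fading reaction reads as improvement. Within that column, a constant between-arm difference of any size up to 3 points is lost entirely, and an excess of d on Day 1 only appears as a benefit of d. These results follow by algebra from the SAP's definitions. The score records are illustrations and imply nothing about how the cream behaves.

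The affected outputs are that column and the Baseline label in Tables 14.3.6.2.1 and 14.3.6.2.2. No test, efficacy result or observed tolerability summary changes. The exception also departs from the SAP's own general rule. The protocol asks only for counts, percentages and mean or median scores by visit, and SAP Section 10 does not list the exception among its changes. It is worth correcting because a planned safety summary does not mean what its heading says.

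**What to change.** 1. Delete the exception in SAP 6.1.1, so that the general rule applies and this assessment has no baseline.
2. In Tables 14.3.6.2.1 and 14.3.6.2.2, rename the Baseline row Day 1 (post-application), fill it from Day 1 records only, and amend the footnotes to match.
3. In Table 14.3.6.2.1, either drop the Change column or retitle it change from first application, with the Day 1 score named as the reference. Base the account of tolerability on observed scores by visit and arm.
4. State one rule for mistimed or missing Day 1 assessments in both SAP 6.1.1 and the footnotes, saying whether the record or the subject is removed.

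The cost is SAP wording and one table shell, with no new data. Dropping the Change column would lose the within-subject view of whether sensation fades, and retitling it keeps that view.
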